### **3 Risk-benefit and ethical considerations**

#### ***3.1 Early insertion of IUC***

Risk: The LNG-IUS 52mg is recommended for immediate insertion only after a surgical abortion in the first trimester according to the manufacturer Bayer. However, the LNG-IUS 19.5mg and 13.5mg are recommended for insertion immediately after any first trimester abortion- the abortion method is not specified. There is no mention of any recommendation for insertion after abortion in the second trimester. The manufacturers recommendation for insertion post partum of all LNG-IUS is after the uterus has reached normal size- earliest at 6 weeks post partum. The recommendation is likely based on the assumption that the uterus might be more sensitive to device perforation, infection or device expulsion immediately after an abortion. However, this is not the case according to current evidence base.

For the copper-IUD the manufacturer recommends insertion “after a first trimester abortion”. The exact timing is not specified nor is the method for abortion. The WHO recommendation are based on research on surgical abortion. There are no studies on insertion of IUC within 48 hours of medical abortion.

The risk with immediate insertion is foremost early expulsion due to contractions in the uterus following the abortion and an open cervix. Expulsions have been shown to be more common after immediate insertion following normal delivery (15) and after immediate insertion in surgical abortion(6).

There has been concern that there may be an increased risk of perforation of the intrauterine device at immediate insertion. However, no such risks have been shown within immediate post partum insertion (15) or immediate post surgical abortion insertion (6). The uterus may quite contrary be thicker and less susceptible to perforation. If the woman experiences abnormal pain at insertion a confirmatory ultrasound will be performed according to clinical practice.

There has also been concern that women may be at increased risk for infection due to residual material and decidua being left in the uterus. This has not been found after immediate post partum insertion where there may be considerable more blood and decidua in the uterus post delivery compared to post abortion(15).

Benefit: LNG-IUS is an established method with a well-known pharmacological profile including side effects also when used post abortion. Intrauterine contraception (IUC) is the contraceptive method with the highest user satisfaction in all age groups (29). LNG-IUS is one of the most effective contraceptive methods (30). Early insertion might reduce the risk of unintended pregnancy post-abortion due to immediate uptake of IUC. Women may also have one less visit to the hospital if the abortion is performed in the hospital and women have the IUC inserted before they leave the premises. It may also decrease the menstrual blood flow and ease menstrual pain in case of LNG-IUS being inserted (31,32). Immediate uptake of LNG-IUS may decrease the amount of bleeding post abortion(8). Insertion within 48 hours post abortion could be less painful because of the dilated cervix.

There is ample evidence on the use of copper IUDs within 48 hours of childbirth which may be considered more similar to a second trimester abortion. Thus, risks and benefits have more studies for copper IUDs. Risk have been considered very small and the benefits of immediate insertion outweigh the risks in the post partum period. We therefore believe that benefits will outweigh risks also for second trimester abortion.

INTRAUTERINE DEVICES (IUDs)			
IUDs do not protect against sexually transmitted infections (STIs), including HIV. If there is a risk of STI/HIV, the correct and consistent use of condoms is recommended. When used correctly and consistently, condoms offer one of the most effective methods of protection against STIs, including HIV. Female condoms are effective and safe, but are not used as widely by national programmes as male condoms.			
CONDITION	CATEGORY		CLARIFICATIONS/EVIDENCE
	I = initiation, C = continuation		
	Cu-IUD	LNG-IUD	
† recommendations reviewed for the MEC 5th edition, further details after this table * additional comments after this table	Cu-IUD = copper-bearing IUD LNG-IUD = levonorgestrel-releasing IUD (20 µg/24 hours)		
POST-ABORTION*			
a) First trimester	1	1	Clarification: IUDs can be inserted immediately after first-trimester, spontaneous or induced abortion.  Evidence: There was no difference in risk of complications for immediate vs delayed insertion of an IUD after abortion. Expulsion was greater when an IUD was inserted following a second-trimester abortion vs a first-trimester abortion. There were no differences in safety or expulsions for post-abortion insertion of an LNG-IUD compared with a Cu-IUD (36–48).
b) Second trimester	2	2	

Table 1. WHO Medical Eligibility Criteria for contraceptive use 2015 Recommended timing of insertion of a LNG-IUS and Cu-IUD

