**Sample size and calculated power**

*Justification of power calculation*

A total of 720 women will be recruited. In order to be able to show a difference of 80 percent in IUC usage in the immediate insertion group at 6 months post insertion compared to 60 percent use in the delayed group with a power of 90 percent and an alpha of 0.05 we would need to randomize 109 women in each group.

If close to 100 percent of women receive the IUC in the immediate group and there is an expulsion rate of maximum 15 percent (immediate post placental insertion after delivery has expulsion rates of 15 percent) and some women have the IUC removed a use of approximately 80 percent could be expected in the immediate group. In the delayed group fewer women are estimated to come for insertion and the expulsion rate is estimated at 5 percent.

We will stratify women in three gestational age categories ( $\leq 9$  weeks+0 days, 9weeks +1 day  $\leq 12$  weeks+0 days, and  $>12$  weeks) to make study data more internationally applicable. We will compensate for surgical procedures due to incomplete abortions and prolonged bleeding which is estimated to be needed in approximately 3-5 percent (13). We will also compensate for a 15 percent loss to follow up which is commonly seen in studies in abortion. Thus, we will randomize 240 women in each gestational strata (total 720 women). Analysis will be presented as intention to treat for all randomized women as well as per protocol for women completing the 6 month follow up (see analysis plan). Follow up at 3, 6 and 12 months will be performed by telephone/email. In women who do not attend FU electronic patient records will be searched for main and secondary outcomes (safety, pregnancy, abortion).

Women will be recruited at several sites in Sweden. Recruitment (numbers) is not expected to be equal at each site but this will be considered in the statistical analysis.

Statistical advice from statistician [name] (adjunct professor and professional medical statistician) has been sought for study design, power calculation, and analysis plan.

Randomization:

The randomization ratio between intervention and control group will be 1:1 in permuted blocks of 4-8 in three strata and per site.

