- The proportion of surgical procedures in total and for each study site (type of procedure, reasons therefore- infection, retained products of conception, prolonged bleeding etc).

Follow up for all women will be by telephone (call) and/or email (by special invitation to a link) with a structured questionnaire with multiple choice questions at 3, 6 and 12 months post abortion when primary and secondary objectives will be reported as described above. Women will answer questions regarding: post abortion bleeding and current bleeding pattern, continued use of IUC/other use of contraception, reasons for non-use of IUC (expulsion, never inserted- reasons, extracted- reason for this), complications (expulsion, infection, surgical intervention

etc), satisfaction with their current contraceptive method and experience of unintended/intended pregnancy and the results of these pregnancies. In addition, patient records in both groups will be reviewed after 6 months in order to extract information concerning possible extra visits related to the abortion or IUC related complications.

Data will be recorded on individual printed case report forms (CRFs), after which they will be entered via a digital case report form (eCRF) using a centre-specific module. Data quality will be assured by both computer-generated verification of consistency and by manual review at monitoring visits. E-CRFs from all sites can only be accessed by the PI and will be transferred into a database. The database will contain information on demographic variables, type of IUC inserted and sound measurement in addition to the variables above.

The end of study is defined as completion of the last visit of the last subject. The sponsor and the investigators reserve the rights to discontinue the study at any time for safety reasons or other reasons jeopardizing the justifications of the study.

An interim analysis of results will be performed when 50 percent of women have been recruited in any gestational strata. If expulsion rates exceed 20 percent or if acceptability rates are below 50 percent by the 3 month follow up the study will be stopped. If the study is prematurely terminated or suspended, the investigator should promptly inform the participants and assure appropriate therapy and follow-up.

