## **9 Study medication**

All women will receive the assigned treatment from the study staff at each site at the time of insertion.

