### ***9.1 Study Medication, dosage and administration***

The following study drugs will be used in the study;

Mirena® (LNG-IUS 52mg),

Kyleena® (LNG-IUS 19.5mg),

Jaydess® (LNG-IUS 13.5 mg),

NovaT 380® (Cu-IUD, medical device, not a drug but due to use outside indication it is included in this application, a separate application for medical device trial has been submitted)

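### No device choice is recorded before open allocation, so the planned analyses by hormonal or copper type rest on a post-randomisation variable that is undefined for women with no insertion

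*Protocol*

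**What the plan says.** **Devices.** Protocol section 9.1 introduces its list with "The following study drugs will be used in the study" and names three levonorgestrel systems and one copper device. No device is limited to one arm. Section 3.1 describes manufacturers' recommendations that differ by device. For the largest hormonal system: "The LNG-IUS 52mg is recommended for immediate insertion only after a surgical abortion in the first trimester according to the manufacturer Bayer". For the two smaller ones: "the LNG-IUS 19.5mg and 13.5mg are recommended for insertion immediately after any first trimester abortion- the abortion method is not specified". For the copper device: "The exact timing is not specified nor is the method for abortion".

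**Entry and allocation.** Section 6.1 asks that the woman opts for IUC, not for a named device. Section 5 (Randomization) has the midwife open a sealed envelope when mifepristone is taken, after eligibility and consent, without blinding. The scheme is: "The randomization ratio between intervention and control group will be 1:1 in permuted blocks of 4-8 in three strata and per site". Device is not a stratum, and naming one is not a precondition for opening the envelope.

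**Supply and recording.** Under section 9 the device is given at insertion, which is within 48 hours in one arm and 2-4 weeks after the abortion in the other. On data, section 5 (Variables and measures) says: "The database will contain information on demographic variables, type of IUC inserted and sound measurement", in addition to the outcome variables listed before it. None of those is the device the woman wanted at randomisation.

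**Analyses that use type.** Section 17.1 compares days of bleeding between groups and also by hormonal or copper use. Its acceptability regression has group, demographic variables and IUC type as explanatory variables.

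**The concern.** A variable fixed before allocation is balanced between arms in expectation and defined for every randomised woman. Type inserted is neither. It is settled after the woman and the staff know the arm, so allocation can influence it, and a woman with no insertion has no value.

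At stake are two secondary analyses. In the bleeding breakdown, women with a hormonal device in the immediate arm would be nearly all who wanted one there. In the delayed arm they would be those who wanted one and came back, plus or minus any who switched. In the acceptability regression, the group coefficient is conditional on a variable that may itself be affected by group, and women without a type drop out of the model. Neither contrast then isolates timing within device type.

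**Working it through.** **1. The plan's own figure.** The claim rests on no stated number, but the sample size is worth confirming. For 80% versus 60%, two-sided 5%, 90% power, pooled variance under the null:

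n = [1.960·√(2·0.70·0.30) + 1.2816·√(0.80·0.20 + 0.60·0.40)]² / 0.20² = (1.270 + 0.811)² / 0.04 ≈ 108.2, rounded up to 109 per group.

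This matches section 17.1 and is unaffected by the point.

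**2. Order of events.**

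| Step | Where | Device choice required or recorded? |
|---|---|---|
| Counselling, consent | Sections 3.3, 15 | IUC in general; no device named |
| Eligibility | Sections 6.1, 6.2 | IUC in general; a woman with a hormonal contraindication may enter by choosing copper |
| Envelope opened | Section 5, Randomization | No |
| Insertion | Section 9 | Device supplied |
| Database | Section 5, Variables and measures | Type inserted |

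The first point at which the protocol provides for a device record for every woman who has an insertion comes after allocation.

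**3. For whom is type inserted undefined?** Inputs from sections 1, 5 and 17.1: insertion close to 100% and expulsion of at most 15% in the immediate arm, with about 80% use at 6 months after some removals; 60% use and 5% expulsion in the delayed arm; 42% not returning for delayed insertion after surgical abortion, a problem that section 1 calls common in medical abortion too. 720 women at 1:1 give 360 per arm.

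- Immediate arm: 1 − 1.00 ≈ 0% without a type.
- Delayed arm, no removals assumed: insertion = 0.60 / 0.95 = 63.2%, so 36.8% without a type (0.368 × 360 ≈ 132 women).
- Delayed arm, removals assumed as in the immediate arm: retention apart from expulsion = 0.80 / 0.85 = 0.941; insertion = 0.60 / (0.95 × 0.941) = 67.1%, so 32.9% without a type (about 118 women).
- Delayed arm, 42% non-return carried over: 42% without a type (0.42 × 360 ≈ 151 women).

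The protocol thus expects roughly 33 to 42% of one arm, and almost none of the other, to have no value for the variable that defines these analyses.

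**4. Is that absence related to outcome?** Section 5 lists heavy bleeding and a change of mind among the reasons for not attempting insertion. The first bears on bleeding days and the second plausibly on acceptability. Restricting to women with a type can therefore select on the outcome, even if nobody's device choice is swayed by allocation.

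**5. Size of any device imbalance.** The shift in an arm contrast would be (difference between arms in device share) × (difference between devices in the outcome). The documents give neither factor. For bleeding the product is not even the right formula, because delayed-arm women have no device in place for the first weeks. No figure is offered.

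**The case against.** The strongest case against runs as follows. The randomised comparison answers the question in section 5, immediate versus delayed insertion, and a change of device after allocation is part of that strategy's effect. The affected analyses are secondary, and section 17.1 already asks for caution with them. Counselling and the choice of IUC precede consent, section 6.2 makes choosing copper a route to entry for some women, and section 2 refers to the IUC the woman intended, so many choices are probably made early. The form is not shown and may have a field for it. How type enters a model is often left to the analysis plan.

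The first two arguments stand and confine the point to the by-type analyses. The others do not remove it. Early choice is plausible, but no text requires it for all women or has it recorded, and an analysis plan cannot recover a choice that was never captured before the envelope was opened.

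A reader might go further and infer from "The LNG-IUS 52mg is recommended for immediate insertion only after a surgical abortion in the first trimester according to the manufacturer Bayer" that staff will choose devices differently by arm, and that bleeding and pain contrasts will be biased as a result. The documents do not support that. Section 3.1 goes on to say that the likely rationale for the labelling is not borne out by current evidence. The WHO table gives hormonal and copper devices the same category in each trimester and reports no difference in safety or expulsion. The label contrast quoted lies mainly among hormonal systems, so a switch prompted by it would leave the hormonal/copper split where it was. Nor does the word assigned in section 9 ("All women will receive the assigned treatment from the study staff at each site at the time of insertion") show that a device is allocated; it is loose wording with no analytic consequence.

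**Conclusion.** The point holds in a limited form. The bleeding breakdown by hormonal or copper use and the acceptability regression on IUC type condition on a variable that follows open allocation. On the protocol's own planning figures that variable is missing for about a third or more of the delayed arm and almost none of the immediate arm. The range of 33 to 42% assumes either that the 60% planning figure reflects non-insertion, 5% expulsion and at most the immediate arm's rate of removal, or that the 42% non-return after surgical abortion carries over.

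The primary outcome and the overall arm comparisons of the secondary outcomes are not undermined by this; they estimate the effect of timing with device as chosen. Whether the device mix will differ between arms is unknown. This is a worthwhile, inexpensive improvement rather than a threat to the trial's main conclusion. It has to be made before randomisation, since the information cannot be reconstructed later.

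**What to change.** In the randomisation text of section 5, require the woman's device choice to be entered on the form before the envelope is opened, stating that it does not bind her and that she may change it later. Add the item to the list of database variables. Log any later change with date and reason.

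In section 17.1, define the hormonal/copper variable for the bleeding breakdown and the acceptability model as the choice recorded before allocation, so that it exists for every randomised woman. Report type inserted, including none, descriptively by arm.

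The cost is one form line and a short wording change, with no extra visit and no restriction on any woman's choice. The drawback is that chosen and inserted device will differ for some women, so results by chosen device describe intention rather than exposure. The descriptive table of type inserted shows how far the two diverge.

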### 3.2 Delayed insertion of IUC

**Risk:** There is a risk for unintended pregnancy possibly followed by an abortion due to a period of several weeks post-abortion without contraception. Women need an additional visit for insertion of an IUC. This need of another appointment to a midwife or doctor might lead to women not attending and as a consequence missing the opportunity to start up with IUC.

**Benefit:** The uterus might be less susceptible to device perforation compared with immediate insertion in the time span 48 hours-2 weeks post abortion but most likely not to insertion within 48 hours post-abortion. The risk of device expulsion may or may not be increased compared to immediate insertion.

### 3.3 Ethical considerations

There is strong evidence that an unintended pregnancy is a potential risk for poor fetal outcome, poor quality relationship between the mother and the child, and adverse effects on mental health (16, 17). A repeat abortion may entail small health risks.

If the results of the study can show that early insertion is superior to standard procedure

concerning use, patient satisfaction and safety, we will have a possibility to offer a highly effective long acting contraceptive method immediately after medical abortion and thereby avoid the risk of unintended pregnancy because of non-attendance for the delayed insertion.

The women will be informed regarding the study at the first visit to the family planning unit. Women can easily decline participation. The free choice to enter and also drop out of the study without having to motivate the decision will be stressed. All women will receive contraceptive counseling and information irrespective of participation in the study or not.

It is important that the individual woman does not feel forced to enter the study. If she chooses another, less effective method she will be offered counselling according to her wishes outside the study. Also, if she is not prepared to make any decision regarding further use of contraceptives this will be respected.

The women will be assured that we do not know the difference in outcome of the study in advance, so that they do not get disappointed when allotted to delayed insertion. Furthermore, it is important not to increase fear of pain related to the insertion, which may make women refrain from showing up at delayed insertion. The hypothesis that immediate insertion is less painful than delayed insertion must not turn to the belief that delayed insertion is more painful than ordinary insertion of an intrauterine device at any other time. It is therefore important that this is correctly described in the information to study subjects.

The main outcome of use of IUC at 6 months post abortion is a surrogate for unintended pregnancy. As IUC is such a highly effective method compared to other methods it is assumed that a higher use of IUC will lead to fewer unintended pregnancies compared to all other methods except sterilization and the implant. This will be stressed at the follow ups but also by scrutinizing the patient records. The participating subjects will be informed both orally and in written before they give informed consent. Abortion could be a very personal question and there might be a risk that the woman can feel that her integrity is affected. The subjects will however be informed before the study starts and before they give their consent. Moreover, all data will be coded and at the time of analysis there will be no possibility to link the information to a specific woman.

## **4 Aim**

This large multicenter, randomized, patient centered clinical trial will investigate the use, safety and acceptability of immediate insertion of intrauterine contraception within 0-48 hours after a completed medical abortion when compared to delayed IUC insertion at 2-4 weeks post abortion which is current practice.

### ***4.1 Primary objective***

The primary outcome measure will be the use of intrauterine contraception at 6 months post abortion in both groups evaluated through follow up by telephone/email.

### ***4.2 Variable***

The proportion of women using IUC as contraception at 6 months post abortion (use vs non-use).

### ***4.3 Secondary objectives***

The secondary objectives are to study if immediate insertion of IUC postpartum is non-inferior to golden standard (insertion 2-4 weeks postpartum) with regard to efficacy, safety and acceptability.

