## Synopsis

### EudraCT:

**Title:** Immediate versus delayed insertion of intrauterine contraception at the time of medical abortion- An open-label, randomized, multicenter study

- Aim** To study use, safety and patient acceptability of intrauterine contraception after immediate insertion compared with standard insertion 2-4 weeks post medical abortion at 3, 6 and 12 months post abortion.
- Drug:** Mirena® (LNG-IUS 52mg), Kyleena® (LNG-IUS 19.5mg), Jaydess® (LNG-IUS 13.5 mg), NovaT® (Cu-IUD, medical device, but due to use outside indication it is included in this application)
- Design:** Open label, randomized, controlled, multicenter study. Phase III (therapeutic confirming).
- Primary objective:** To study if immediate insertion of intrauterine contraception is superior to insertion at 2-4 weeks post abortion with regard to number of women using IUC as contraception at 6 months post abortion.
- Variable:** The proportion of women in each group (immediate or delayed) using IUC as contraception at 6 months post abortion (use vs non-use).
- Secondary objectives:** To study if immediate insertion of intrauterine contraception is non-inferior to delayed insertion with regard to safety and acceptability.

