Post partum is also a sensitive period for unplanned and unwanted pregnancy. Insertion of IUC immediately after placental expulsion in childbirth results in lower rates of expulsion compared to insertion after 48 hours. Expulsion at immediate insertion post partum has been estimated at 15 percent.(10) The expulsion rate of IUC at delayed insertion has been shown to be 5 percent.(6) The approach of immediate IUC insertion post medical abortion has not been explored. There have been concerns that immediate post medical abortion IUC insertion may increase IUC expulsions due to bleeding and contractions or increase the risk of infection.

Our previous studies on the development of medical abortion, reduction of the number of visits for abortion and increased access to safe abortion through simplified medical abortion have had great impact on implementation and guidelines in Sweden and worldwide (11-13). However, there is an urgent need to update guidelines on post medical abortion IUC insertion where evidence based recommendations are lacking(14).

The rationale for this study is the hypothesis that a greater proportion of women undergoing medical abortion – close to 100 percent - will receive their intended post abortion IUC if it is inserted within 0-48 hours of the expulsion of the placenta compared with routine insertion at a scheduled follow up visit 2-4 weeks later. This could more than well compensate for a possible slightly higher rate of IUC expulsion and will reflect in a higher usage rate at 6 months following the abortion. If shown to be successful immediate IUC insertion will help women avoid subsequent unplanned and unwanted pregnancy following the abortion.

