### ***4.4 Variables***

#### **4.4.1 Efficacy, acceptability:**

- Difference in the proportion of women who successfully have the IUC inserted (success versus failure),
- Continued use of IUC at 3 and 12 months post insertion evaluated by telephone/email follow-up (continued use/voluntary discontinued use, involuntary discontinued use including expulsions etc) reasons for discontinuation will be recorded and subsequent use of other contraceptive methods will be noted)
- Ease of insertion according to health care provider (judged as very easy, easy, moderately, or very difficult)
- pain at time of insertion (women will indicate the pain before insertion, at placement of tenaculum, sound and IUC by putting a vertical mark on a 10 cm long horizontal line with

a Visual Analogue Scale (VAS) from 0, indicating no pain to 10 indicating worst imaginable pain. Result will be noted in millimeters and entered into case report forms).

- Post-abortion bleeding (number of days of fresh bleeding and spotting after the abortion)
- Reasons for non-attempted insertion of IUC (change of mind, heavy bleeding, not coming for insertion, staff being unavailable etc),
- Pregnancies occurring during the 12 month follow-up (planned and unplanned, wanted and unwanted, pregnancy outcomes- ectopic, miscarriage, abortion, molar, kept pregnancy),
- Acceptability of immediate and delayed insertion of IUC by asking women if they would recommend the procedure to a friend (yes/no, asked at the time of insertion and at the 3, 6 and 12 month follow up),
- Acceptability of IUC as post abortion contraception- evaluated as above,

[figure not shown]

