## **5 Design**

The study protocol is designed as a superiority trial according to the recommendations in the CONSORT statement for randomized superiority trials ([www.consort-statement.org](http://www.consort-statement.org)). It is defined as a Phase III trial (therapeutic confirming).

The flow of patients is presented in this flowchart.

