Randomization will be performed by the midwife in the family planning/ abortion clinic at the time of intake of mifepristone after the patient has been judged eligible for participation and has signed informed consent in the presence of the attending physician. Allocation to intervention or control will be performed via opening of opaque sealed envelopes in consecutive order. Each site will have a separate randomization sequence. All women will be identified through a patient log with name and Swedish personal identification number and the randomization number. The randomization number will be used on all paper and eCRFs. The study will for practical and ethical reasons not be blinded. The medical abortion will be performed according to the Swedish national guidelines.

Choice of study design:

The project will be performed as a randomized, controlled, multicenter superiority trial. It is known that sociodemographic factors such as parity and age may influence the choice of contraception and the rate of continued use. The rate of expulsion may be influenced by parity and gestational length. To eliminate these confounders the randomized design is superior. Many of the factors studied such as the primary outcome are objective and should not be affected by the non-blinded design. It is not deemed feasible to do a single blinded study where the health care provider would be blinded to the insertion time as the women with immediate insertion will likely be bleeding more than the women with delayed insertion. The women with immediate insertion will also have an open outer cervical os. Therefore, the health care provider would likely be affected by these findings at the IUC insertion.

**Primary outcome** will be the use of IUC at 6 months follow up. A difference of 20 percent between the study groups (immediate versus delayed insertion) will be considered as clinically significant (please see justification for power calculation).

**Secondary outcomes** include the rate of IUC inserted, rate of expulsion, pain at insertion, bleeding, reasons for non-insertion of IUC, IUC use, complications, acceptability, pregnancies and abortions evaluated at 3 and 6 months follow up and annually up to five years.

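### Section 4.3 places efficacy under a non-inferiority aim (and says postpartum), against the synopsis, the superiority design and the difference tests planned in 17.1

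*Protocol*

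**What the plan says.** The protocol gives the secondary objective in two forms.

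- Section 4.3 asks whether immediate insertion is "non-inferior to golden standard (insertion 2-4 weeks postpartum) with regard to efficacy, safety and acceptability". It uses the word postpartum for both the immediate and the delayed insertion.
- The synopsis asks whether it is "non-inferior to delayed insertion with regard to safety and acceptability". Efficacy is not in that list.

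Elsewhere, IUC use is a superiority question. The synopsis gives the primary objective as "To study if immediate insertion of intrauterine contraception is superior to insertion at 2-4 weeks post abortion", with 6-month use as the outcome. Section 5 says "The study protocol is designed as a superiority trial", and later in the same section: "A difference of 20 percent between the study groups (immediate versus delayed insertion) will be considered as clinically significant". Section 17.1 sizes the trial for 80% against 60% use.

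Within section 4 the direction is less clear. Section 4.1 says "The primary outcome measure will be the use of intrauterine contraception at 6 months post abortion in both groups", which names an outcome but no hypothesis. Section 4.4.1, headed as efficacy and acceptability, lists the variables that serve 4.3. They include successful insertion and "Continued use of IUC at 3 and 12 months post insertion evaluated by telephone/email follow-up".

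Section 17.1 plans Fisher's exact test for the primary outcome and for insertion success. For outcomes measured at several time points, it plans a global permutation test built from Fisher tests at each time point. No non-inferiority margin appears anywhere.

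**The concern.** Objective, design and analysis should ask the same question. For the secondary efficacy outcomes they do not. Section 4.3 asks whether immediate insertion is no worse, while the design and the tests ask whether the arms differ. Insertion success and IUC use at 3 and 12 months are closely tied to the primary outcome, so readers will take them together with the 6-month result.

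Suppose the 6-month comparison fails. Section 4.3 as worded then leaves room to describe a non-significant secondary difference as non-inferior efficacy. A non-significant test of difference does not establish non-inferiority. That needs a margin fixed in advance and a confidence limit set against it.

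Such a claim would also sit badly with the stated rationale, that near-complete uptake will outweigh extra expulsions: "This could more than well compensate for a possible slightly higher rate of IUC expulsion". A finding of no worse use does not test that expectation.

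**Working it through.** **1. Is the plan's own sample size a superiority calculation?**

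Inputs from section 17.1: 80% and 60% use, power 90%, alpha 0.05, 109 per group. Sidedness is not stated, so two-sided is tried. With mean proportion 0.70:

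n = [1.96 × √(2 × 0.70 × 0.30) + 1.2816 × √(0.80 × 0.20 + 0.60 × 0.40)]² / 0.20²

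= [1.96 × 0.6481 + 1.2816 × 0.6325]² / 0.04 = (1.270 + 0.811)² / 0.04 = 108.2, rounded up to 109.

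This matches exactly. The figure is a two-sided superiority calculation with no margin in it. One-sided testing would give 89, and a continuity correction 119.

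**2. The statements side by side**

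| Place | Question asked about IUC use or efficacy |
|---|---|
| Synopsis, primary objective | Superiority at 6 months |
| Synopsis, secondary objective | Non-inferiority on safety and acceptability only |
| Section 4.1 | Outcome named, no direction |
| Section 4.3 | Non-inferiority on efficacy as well |
| Section 5 | Superiority trial |
| Section 17.1 | Tests of difference, no margin |

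Only 4.3 names efficacy in a non-inferiority aim, and no planned test serves it.

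**3. How easily could a non-inferiority criterion be met with no gain?**

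The protocol gives no margin, so those below are assumptions. Other inputs: true use of 60% in both arms (the planned delayed-arm rate at 6 months), and 720 women randomised 1:1, so 360 per arm. Less the 15% allowance for loss, 360 × 0.85 = 306 per arm.

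SE = √(2 × 0.60 × 0.40 / 306) = 0.0396

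P(lower 95% limit above −margin) = Φ(margin / SE − 1.96)

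- 5 points: Φ(1.26 − 1.96) = 0.24
- 10 points: Φ(2.52 − 1.96) = 0.71
- 15 points: Φ(3.79 − 1.96) = 0.97

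Under the same truth, superiority of immediate insertion would be declared in about 2.5% of trials.

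In a single gestational stratum, 120 × 0.85 = 102 per arm, and SE = √(0.48 / 102) = 0.0686. The same margins give 0.11, 0.31 and 0.59.

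If immediate insertion were truly 5 points worse (55% against 60%, 306 per arm), SE = √((0.2475 + 0.24) / 306) = 0.0399. The chances are then 0.025, 0.24 and 0.71.

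These figures borrow the 6-month rate and the general loss allowance for a claim about 3 or 12 months. They are an illustration, not a forecast. They give the chance of clearing a margin of the stated size, not the chance that such a claim would be made.

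**The case against.** Much can be said for treating this as a wording slip.

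- **The main claim is protected.** A reader might infer that a trial with no gain in use could report its efficacy objective as met. The documents do not support that. The primary objective is superiority at 6 months, tested for a difference, and a null trial misses it whatever 4.3 says. This stands and limits the point to secondary outcomes.
- **No planned test delivers non-inferiority.** There is no margin, and for outcomes at several time points a non-significant global test bars any significant finding at a single one. This stands too. The risk is a loose or post hoc claim, not a formal one.
- **The hypotheses are not opposites.** Superiority implies non-inferiority and points the same way. The fault is a mismatch between objective and analysis, not a logical contradiction.
- **Equal use would not by itself defeat the rationale.** A reader might infer that immediate insertion is worthwhile only if use rises. Section 3.1 names other possible benefits: earlier protection, one visit fewer, less pain at insertion, less bleeding with a hormonal device.
- **Efficacy may mean something else.** Section 17.1 lists abortion rate first among the secondary efficacy outcomes, and non-inferiority there would be an intelligible aim. But 17.1 tests it for a difference as well, and 4.4.1 puts insertion success and IUC use in the same list.
- **The synopsis is not a clean model.** It too lists insertion success and IUC use as efficacy and acceptability variables straight after its non-inferiority aim. Deleting one word from 4.3 is therefore not enough.
- **Postpartum is a drafting slip.** The rest of section 4 concerns medical abortion, and no enrolment or analysis depends on the word.

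**Conclusion.** The point holds in a limited form. Section 4.3 states a non-inferiority aim for efficacy that the synopsis does not share, the design and sample size do not support, and the tests in 17.1 cannot answer. It also names the wrong setting, which alone would be editorial.

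The primary 6-month objective and the figure of 109 per group are not affected. At stake is the reporting of insertion success and of IUC use at 3 and 12 months, where a non-significant difference could be presented as non-inferior efficacy.

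The size cannot be fixed from the documents. With equal 60% use and 306 per arm it runs from about 24% to 97% over assumed margins of 5 to 15 points, and it is lower within one stratum. The case for correction rests on the mismatch itself, not on any one of these percentages. The change should be made because it is nearly free and aligns objective, design and analysis.

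**What to change.** In section 4.3, delete efficacy from the non-inferiority aim so that it matches the synopsis, and replace postpartum with post abortion in both places. In both 4.3 and the synopsis, add that insertion success and IUC use at 3 and 12 months are assessed for superiority by the difference tests in section 17.1. The added statement matters as much as the deletion, because the synopsis has the same ambiguity in its list of variables.

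The cost is a short amendment to the wording. Sample size, conduct and planned tests do not change. The downside is that the sponsor gives up a fallback secondary efficacy claim.
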